Designated testing rooms are available in the ORP for consenting, paper-pencil testing, and computer testing. A ventilated smoking suite, approved by the fire and safety administration at Spring Grove Hospital, is available in the TRP. The room is private, ~169 square feet, and is designed to house computer equipment. A slot in the door allows passing through materials. The TRP also houses a dayroom equipped with TV, DVDs, books, magazines, and internet access.

3 * Describe the availability of medical and/or psychological resources that subjects might need as a result of anticipated consequences of the human research:

A study nurse will be on site, and a physician familiar with the study will always be on call. Medical equipment is available in the nurse's station. In the case of any medical emergency, medical services would be called and the participant transferred to a hospital. Should a participant experience any distress, the PI, nurses, psychiatrists, and social workers are on site and could speak with them.

4 * Describe the process to ensure that all persons assisting with the research are adequately informed about the protocol, the research procedures, and their duties and functions:

As part of protocol implementation, a Study Manual will be distributed to all persons involved, detailing Standard Operating Procedures for each person's role in the study, procedures to be followed in the case of any emergency, and emergency contact numbers. Prior to recruitment, all persons involved will meet, and the Principal Investigator will describe all procedures and sequences of events and answer any questions.

ID: VIEW4DF83CB976400
Name: v2_Resources

Sites Where Research Activities Will Be Conducted

1 * Is this study a:

Multi-Site
 Single Site

2 * Are you relying on an external IRB (not UM) to be the IRB of Record for this study?

Yes No

3 * Are any other institutions/organizations relying on UM to be the IRB of Record for this study?

Yes No

3.1 Attach the applicable regulatory documents here (i.e., IRB Authorization Agreement (IAA), FWA, local ethics approval, other IRB approvals, etc.). Final UM approval will be contingent upon final execution of all required regulatory approvals:

Name	Created	Modified Date
------	---------	---------------

There are no items to display

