A factor which may facilitate such stimulus-controlled smoking routines in PSZ is that smokers with schizophrenia (SmoSz) appear remarkably insensitive to subjective effects of nicotine. According to theories of drug dependence, drug effects insensitivity would facilitate a habitual, cue-locked drug taking mode.

Furthermore, automatized drug-taking is reportedly associated with frontoexecutive control deficits, a hallmark of the neurocognitive profile of schizophrenia. Thus, nicotine insensitivity and cognitive control deficits may facilitate automatized, stimulus-driven smoking in SmoSz.

The overall aim of this proposal is to determine whether tobacco smoking in PSZ is under disproportionately strong cue control, and to test whether insensitivity to the subjective effects of nicotine and/or cognitive control deficits can account for this.

Aim 1 is to test whether tobacco smoking behavior is under greater cue control in SmoSz than in matched healthy control smokers (SmoCon). Approach: Indices of cue-controlled smoking are obtained by quantifying the degree to which virtually nicotine-free cigarettes can maintain smoking behavior over eight hours under standardized laboratory conditions, in the presence of transdermal nicotine replacement. Nicotine-free cigarettes evoke a near-complete set of internal and external stimuli and behavioral routines associated with tobacco smoking, but without ensuing nicotine delivery, thus capturing the essence of stimulus control over smoking behavior.

Aim 2 is to test whether SmoSz are less sensitive to the subjective effects of nicotine than SmoCon. Approach: In a standardized laboratory paradigm, SmoSz and SmoCon discriminate research cigarettes of differing nicotine yields, and report on subjective state measures after each cigarette.

Aim 3 is to determine whether nicotine insensitivity is related to cue-control over smoking behavior, and can account for the group difference therein.

Aim 4 is to determine whether cognitive control deficits are related to cue-control over smoking behavior, and can account for the group difference therein. Approach: A cognitive control index will be derived from tasks selected from the RDoC matrix.

2 * Discuss the research design including but not limited to such issues as: probability of group assignment, potential for subject to be randomized to placebo group, use of control subjects, etc.:

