Smokers with and without a diagnosis of schizophrenia or schizoaffective disorder will undergo the same laboratory research protocol (4 sessions). Nicotine sensitivity and cue-controlled smoking behavior will be compared between these groups and correlated within groups.

3 * Describe the relevant prior experience and gaps in current knowledge. Describe any relevant preliminary data:

Nicotine's abuse liability is comparable to other drugs of abuse despite relatively weak primary reinforcing effects(7-12). Substituting nicotine causes only small reductions in smoking(13, 14), and nicotine replacement is relatively ineffective in quit attempts(15). Conversely, denicotinized cigarettes maintain a level of smoking, satisfaction, relaxation, and craving relief(16-18). Thus, acute pharmacological effects cannot fully explain nicotine's dependent use. Instead, plentiful evidence suggests that tobacco dependence is marked by automatized, cue-locked behavior. Environmental and physiological stimuli associated with nicotine intake exert powerful control over tobacco consumption, elicit craving and autonomic responses, capture attention, and precipitate relapse(19-30). Consistent with behavioral automaticity, cue-induced cigarette smoking becomes resistant to nicotine devaluation by satiation(31, 32). Rat self-administration studies concur that stimuli paired with nicotine infusions promote acquisition of nicotine seeking, slow its extinction, and reinstate it(33-35). In direct comparison, cue delivery had greater influence over nicotine-seeking than nicotine delivery itself(33).

Influential theories of addiction based on clinical and preclinical evidence state that the rise of an automatized, cue-locked drug seeking mode and a concomitant decline in awareness of the drug's specific subjective effects are central to the transition to dependence(36, 37). Interestingly, a study in rats employing cocaine showed that heightening the sensitivity to subjective drug effects by discrimination training slowed the acquisition of its self-administration on a higher-order schedule(38).

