After the last discrimination trial, a breath CO reading (x2) is taken, and participants are asked to smoke one research cigarette (A or B) of their choice (not through the CReSS, to create more naturalistic conditions). Choice is recorded. Independent thereof, participants will always be given the VLNC cig. Another CO breathalyzer measurement is taken immediately after smoking to measure the CO-boost from this cigarette, and participants complete the MTWS, AWS, QSU, and mCEQ one last time.

4. Ad Libitum Smoking Session (~8.5 hrs), scheduled ≥ 2 days after the Discrimination Session:

Participants are instructed not to smoke or ingest any nicotine-containing products from waking up until session start at ~9 am, verified by expired CO ≤ 7 ppm. If the CO threshold is exceeded, the session may be rescheduled. Female participants also provide a urine sample for repeat pregnancy testing, which would end participation.

Anicotine patch is then applied (21 mg/24 hrs; if previously not tolerated: 14 mg/24 hrs). Participants deposit their own cigarettes with the research assistant, and a box of VLNCcigs is provided. More VLNCcigs will be dispensed if needed - smoking is ad libitum. Participants are not told that the research cigarettes are virtually nicotine-free, but the consent form states that research cigarettes and patches may differ in nicotine yield from conventional products. For the next 8 hrs, participants stay at the MPRC, settled in a ventilated fire-proofed smoking room with access to the internet and DVDs. In the first hour, breakfast is offered, at noon, lunch is provided, at 3 pm a light snack. The research assistant's desk is adjacent to the smoking room, separated by a semitransparent window; he is available throughout the day. The research assistant records the time of each smoke, and the number of VLNCcigs smoked each time. After 8 hrs, another breath CO breathalyzer reading ($\times 2$) is obtained - the main outcome variable. The secondary outcome, the decline in VLNCcig smoking across the session, is obtained by subtracting the total number of VLNCcigs smoked in the last 2 hrs from that smoked in the first 2 hrs.

2 * Describe all procedures already being performed for diagnostic or treatment purposes (if not applicable to the study, enter "N/A"):

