5.1 If Yes, what procedures are in place to assure safety?

If a participant were to disclose his or her intent to harm him- or herself or others, the participant will be escorted to a psychiatrist, to a social worker, or to another clinician at the MPRC for an immediate evaluation. These clinicians will then determine appropriate action and follow-up depending on the circumstances.

ID: VIEW4E0947A633C00
Name: v2_Interviews

Observation

You indicated that this study involves individual or group behavioral observations.

1 * Please describe what is being observed.

Ad libitum smoking of very low nicotine content cigarettes (VLNCcigs) for 8 hours at the MPRC while wearing a nicotine patch. Participants spend their time in a day room and walk to a smoking room whenever they wish to smoke VLNCcigs. The number of smoked cigarettes is recorded, and participants exhale into a CO breathalyzer (see Study Procedures for details).

2 * Are any of the observations likely to cause harm if confidentiality were breached? (i.e., Illegal activities)

Yes No

3 * How will individuals identities be protected?

All outcome measures are recorded on forms labeled with only subject ID code, study number, date, and subject and rater initials. No video or audio recordings are taken.

4 * How will observations be recorded?

On paper forms not containing the subject's name or other PII.

ID: VIEW4E0BBF1EF0400
Name: v2_Observation

Testing

You indicated that this study involves neuropsychological or psychophysiological testing.

If you uploaded a separate research protocol document in the 'Research Protocol' page, cite the applicable section and page numbers from that document in the answer boxes below.

- 1 * List all of the tests to be used in the study, including both standardized and non-standardized assessments:
 - Two computerized tasks will be performed:
 1. ExpectancyAX-CPT
 2. Stroop paradigm
 - 3. The WASI Vocabulary and Matrix Reasoning subtests to assess intellectual competence
 - 4. The Reasoning/Problem Solving subscale of the MATRICS Consensus Cognitive Battery (MCCB)
 - 5. Wechsler Test for Adult Reading (WTAR)
- 2 * Describe procedures related to all testing:
 - Computerized ExpectancyAX-CPT: Atrial consists of the letters A or B (contextual cue) followed by an X or Y. The default after each letter is a non-target response; only an X that was preceded by an A requires a target response. After the Acue, there is an 80% chance that an X will follow.

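### Does it matter that the 8-hour Ad Libitum Smoking Session is described with two different room set-ups?

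*Combined protocol and SAP*

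**What the plan says.** Study Procedures, item 1, part 4, sets out the session in operational detail: morning abstinence checked by expired CO, a nicotine patch, very low nicotine cigarettes supplied without limit, meals at set times, a research assistant at a desk next to the smoking room who logs each smoke, and a repeated breath CO reading after 8 hours. On location it says that "participants stay at the MPRC, settled in a ventilated fire-proofed smoking room with access to the internet and DVDs".

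The Observation page, item 1, summarizes the same session (8 hours, ad libitum, patch on) but says: "Participants spend their time in a day room and walk to a smoking room whenever they wish to smoke VLNCcigs". It continues: "The number of smoked cigarettes is recorded, and participants exhale into a CO breathalyzer (see Study Procedures for details".

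The description of the research laboratory setting lists two spaces. Of the smoking suite it says: "The room is private, ~169 square feet, and is designed to house computer equipment". Of the other: "The TRP also houses a dayroom equipped with TV, DVDs, books, magazines, and internet access".

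Aim 1 defines the target as the degree to which "virtually nicotine-free cigarettes can maintain smoking behavior over eight hours under standardized laboratory conditions". The design statement (Justification, Objective, & Research Design, item 2) says that smokers with and without schizophrenia "will undergo the same laboratory research protocol". The resources section adds that "a Study Manual will be distributed to all persons involved, detailing Standard Operating Procedures".

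**The concern.** A participant settled in the smoking room for the day does not also sit in a day room and walk over for each cigarette. The two sentences describe different arrangements of one session, and neither is marked as superseding the other.

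The point attracts attention because of what the session measures. Aim 1 is about control of smoking by cues, and the background section argues that environmental stimuli strongly govern tobacco use. Sitting all day in a room meant for smoking, or having to leave another room to smoke, could alter both the exposure to cues and the effort per cigarette. On the protocol's own reasoning the setting might influence the 8-hour CO reading and the change in cigarette counts from the first 2 to the last 2 hours. If staff applied the two descriptions unevenly, and unevenly by diagnosis, the main comparison could be confounded. Short of that, a reader wishing to repeat the session could not tell from these pages where participants sat.

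**Working it through.** The plan has no figure on this point to reproduce. The sample size calculation does not use the room set-up, and the documents contain no data on its effect. The check is a comparison of texts, followed by the consequence for the analysis.

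**1. Is it the same session?** Yes. Both texts give 8 hours of ad libitum smoking of very low nicotine cigarettes with a nicotine patch.

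**2. Can the texts be read together?** No. The smoking suite and the dayroom are listed as separate facilities.

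**3. Which text carries more weight?**

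| Feature | Study Procedures | Observation |
|---|---|---|
| Purpose | step-by-step conduct | short answer to a form question |
| Where participants stay | smoking room | day room |
| Where smoking takes place | smoking room | smoking room |
| Observer's position | desk beside the smoking room | not given |
| Abstinence check, meals, CO timing | given | not given |
| Cross-reference | none | to Study Procedures |

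The weight falls on Study Procedures. The suite is said to be built to house computer equipment and has a door slot for passing materials, which fits a long stay. Against that, the facilities text places DVDs and internet in the dayroom, so the question is not fully settled. Stale wording is known elsewhere in the form: the Testing page, item 2, times an assessment relative to giving a lozenge, and this study has none. A leftover sentence on the Observation page is therefore plausible, though unproven.

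**4. What happens to Hypothesis 1?** The test is a two-sample t-test on breath CO (ANCOVA if matching is poor). Let the group means under a reference set-up be m1 and m2, and let the set-up actually used shift CO by s.

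- One set-up for all, equal shift: (m1 + s) − (m2 + s) = m1 − m2. The contrast is unchanged.
- One set-up for all, shifts s1 and s2 that differ by group: the contrast is (m1 − m2) + (s1 − s2). It is still a valid group difference under the conditions used, and its size is specific to those conditions.
- Set-up varying between participants but unrelated to group: no bias on average, some added variance.
- Set-up varying by group: confounded. Nothing in the documents points to this, and the design statement gives both groups the same procedures.

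**5. Scope.** Hypothesis 1 names breath CO from this session. Hypothesis 3 refers only to cue control, and Hypothesis 4 is tested analogously. That they rest on this session is a fair inference, and that they use breath CO in particular is not stated. On that reading 3 of 4 hypotheses draw on the session, in 45 × 2 = 90 planned completers. These counts say how widely the session is used, not how far a result could move.

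**The case for a change.** The strongest case for acting is that this is the main-outcome session, that the conditions are meant to be standardized, and that setting is part of the construct when the construct is cue control. A cross-reference for details should lead to elaboration, not contradiction. It also follows the sentence on counts and CO, so it may not cover the room at all. A one-sentence correction is cheap.

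Much of this stands. The texts do conflict, and the set-up cannot be established with certainty from the documents. What does not stand is the step to a defect in the trial. It would go too far to say that the session cannot be reproduced or its values interpreted: abstinence, patch, cigarettes, duration, meals, recording and the CO reading are all specified, and only the place where participants wait between cigarettes is in doubt. Under both texts they smoke in a smoking room. Confounding by set-up is hypothetical. The Study Manual, which details standard operating procedures, is not among the documents and may already settle the matter. Cheapness is no reason to amend when the correction would favor neither arrangement and leave every analysis as it was.

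**Conclusion.** This is a real inconsistency of wording, best regarded as a clerical slip on a form page, and no change to the plan follows. The size of any room effect on breath CO is unknown, and none is assumed. The effect on the validity of the Hypothesis 1 comparison is nil provided that one set-up serves both groups, as the design statement implies. Study staff would naturally work from Study Procedures and the Study Manual, and a competent report of the trial would describe the room in its methods as a matter of course.

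The conclusion rests on two assumptions: that both groups were run under the same arrangement, and that the unseen Study Manual does not direct otherwise. Evidence that the room differed by diagnosis would reopen the question, but the documents contain none.

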Some participants may already have done a SCID in the context of clinical care or another study. If this SCID was done at the MPRC, it will not be redone. The diagnostic information will have entered clinical records and will be accessed under a partial HIPAA privacy waiver.

3 * Describe the duration of an individual participant's participation in the study:

The shortest time within which the study can be completed by any participant is 1 week. A maximum of 3 months may expire between any of the four sessions described above (although efforts will be made to not exceed 2 weeks). Thus, the maximum completion time is 9 months.

4 * Describe the amount of time it will take to complete the entire study:

The is a two-year study.

5 * Describe any additional participant requirements:

None.

ID: VIEW4E0280585B400
Name: v2_Study Procedures

Sample Size and Data Analysis

If you uploaded a separate research protocol document in the 'Research Protocol' page, cite the applicable section and page numbers from that document in the answer boxes below.

1 * Provide the rationale and sample size calculations for the proposed target population:

Power analyses indicate that, at $\beta=0.8$, $N=45$ per diagnostic group would enable detection of medium effect sizes (Cohen's $d=0.6$, Cohen's $f=0.3$) with the analyses described below. To prepare for a 20% attrition rate, we will randomize 112 participants for 90 completers. Based on an expected 20% screening failures, we anticipate that screening 140 volunteers will result in 112 enrollments, but to be on the safe side, we set the enrollment ceiling at 160.

2 * Provide the plan for data analysis. Include in the description the types of comparisons that are planned (e.g., comparison of means, comparison of proportions, regressions, analysis of variance, etc.), which is the primary comparison/analysis, and how the analyses proposed will relate to the primary purposes of the study:

- Hypothesis 1 (smoking is under greater cue control in SmoSz than SmoCon) is tested by two-sample t-test comparing groups on breath CO after 8 hrs of ad libitum VLNCcig smoking (ANCOVA if group matching is suboptimal for 1 or more variables). Secondary analysis: ANOVA (or ANCOVA) to compare groups on the number of VLNCcigs smoked in the first vs. last 2 hrs of the Ad Lib Smoking Session (group x time point).

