- Hypothesis 2 (SmoSz are less sensitive to subjective nicotine effects than SmoCon) is tested by two-sample t-test (or ANCOVA) comparing nicotine discrimination accuracy between groups. Secondary analysis: The composite subjective state score after smoking a VLNC or a 0.8 mg-yield cigarette is compared between SmoSz and SmoCon by ANOVA (group x cigarette type), or ANCOVA if indicated (see above).

- Hypothesis 3 (nicotine sensitivity is related to cue control and can account for the group difference therein): Regression analysis tests the impact of discrimination accuracy on cue control while controlling for the group effect. To evaluate the degree to which nicotine insensitivity can statistically account for the group difference in cue-control, we measure the reduction in the group effect when entering discrimination accuracy, with a >25% reduction in β group defined as significant. To determine the percentage of between-group variance in cue control statistically accounted for by nicotine sensitivity, we quantify the reduction in variance explained by the group factor when including discrimination accuracy as a covariate in ANCOVA.

- Hypothesis 4 (cognitive control deficits can account for cue-control and for the group difference therein) is tested in a manner analogous to Hypothesis 3.

ID: VIEW4E02806052800
Name: v2_Sample Size and Data Analysis

Sharing of Results

1 * Describe whether results (study results or individual subject results, such as results of investigational diagnostic tests, genetic tests, or incidental findings) will be shared with subjects or others (e.g., the subject's primary care physicians) and if so, describe how it will be shared:

If significant abnormalities are identified during screening, these test results would be given to the subject, together with a recommendation regarding the appropriate type of follow-up (e.g., see family doctor or specialist). With written authorization from the participant, test results may also be shared with their care provider.

The overall trial outcome would not be shared with individual participants or their providers but will be made accessible via scientific publication.

ID: VIEW4E02808CBD800
Name: v2_Sharing of Results

Research with Drugs or Biologics

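### The 80% power statement covers every planned analysis, but at the stated effect sizes it does not extend to the >25% rule in Hypotheses 3 and 4

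*Combined protocol and SAP*

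**What the plan says.** Item 1 of Sample Size and Data Analysis makes a single power statement. It says that 45 completers "per diagnostic group would enable detection of medium effect sizes", given as d=0.6 and f=0.3, at power of 0.8 (printed as β=0.8, read here as 1−β), and claims this "with the analyses described below". No analysis is excepted. Allowance for dropout is stated: "To prepare for a 20% attrition rate, we will randomize 112 participants for 90 completers".

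Item 2 then lists the analyses:

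- Hypothesis 1: "two-sample t-test comparing groups on breath CO after 8 hrs of ad libitum VLNCcig smoking".
- Hypothesis 2: a two-sample t-test "comparing nicotine discrimination accuracy between groups".
- Hypothesis 3 has two main parts. A regression tests the slope of cue control on discrimination accuracy, adjusted for group. A separate rule then decides whether accuracy accounts for the group difference, "with a >25% reduction in β group defined as significant". An estimate of the share of between-group variance explained accompanies them.
- Hypothesis 4 repeats this with the cognitive control measure as mediator.

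The plan gives no size for the mediator-outcome association, no group difference for the cognitive control index, and no power figure for the 25% rule.

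**The concern.** Aims 3 and 4 ask whether nicotine insensitivity or cognitive control deficits can account for the group difference in cue control. The 25% rule supplies the yes/no answer, and the plan itself attaches the word significant to it. A reader of item 1 would therefore take that answer to have 80% power.

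The rule compares an estimated ratio with a fixed cut-off, so its chance of success depends on how far the true fall lies above 25%. It need not match the power of a t-test or a slope test at the same sample size. If the true fall is only a little above 25%, a real mediator will often miss the threshold, and the miss could be mistaken for well-powered evidence against mediation.

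**Working it through.** **Inputs from the plan:** 45 completers per group (112 × 0.8 = 89.6, about 90 in total), d=0.6, f=0.3, power 0.8, cut-off 25%.

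**Assumed:** two-sided alpha of 0.05, since none is stated beside the power claim. A one-sided test would give 0.88, so two-sided 0.05 is what matches the plan.

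**Step 1. Reproduce the stated figure.**

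- Two-sample t-test: noncentrality d√(n/2) = 0.6 × √22.5 = 2.85 on 88 df, power 0.804.
- Two-group ANOVA at f=0.3, N=90: power 0.804.
- One regression slope with group in the model, if f=0.3 is its effect size: λ = f²N = 0.09 × 90 = 8.1, F(1, 87), power 0.804 (0.79 by simulation).

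The 80% is therefore correct for these tests.

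**Step 2. Expected fall under the 25% rule.** Let c be the group difference in breath CO, a the group difference in the mediator, and b the mediator slope adjusted for group. In least squares the fall in the group coefficient is c − c′ = ab, so the proportional fall is ab/c.

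Apply the stated sizes to every path, with within-group SDs of 1. Then c = 0.6 and a = 0.6. Taking f=0.3 for the slope, the within-group correlation is r = √(0.09/1.09) = 0.287, so b = 0.287. The expected fall is 0.6 × 0.287 / 0.6 = 28.7%, just above the cut-off.

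**Step 3. Probability of meeting the rule** (200,000 simulated trials, 45 per group):

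| Event | Probability |
|---|---|
| Group difference in CO significant | 0.80 |
| Slope significant | 0.79 |
| Estimated fall >25% | 0.57 |
| Fall >25% and slope significant | 0.53 |

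**Step 4. Sensitivity to what the plan does not state** (rule alone, 45 per group, d=0.6 on CO):

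| Mediator difference d | Within-group r | Expected fall | Rule met |
|---|---|---|---|
| 0.6 | 0.20 | 20% | 34% |
| 0.6 | 0.287 | 28.7% | 57% |
| 0.6 | 0.40 | 40% | 81% |
| 0.6 | 0.50 | 50% | 93% |
| 0.8 | 0.287 | 38% | 76% |
| 1.0 | 0.287 | 48% | 87% |

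At r=0.20 the true fall is itself below 25%, so that row gives how often the rule is met, not power in the usual sense.

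**Step 5. Would more participants help?** At d=0.6 and r=0.287 the rule is met in 63% of trials with 100 per group, 69% with 200 and 79% with 500. The limiting factor is the closeness of 28.7% to 25%. With no mediator effect (b=0) the rule alone is met in about 4% of trials, so false positives are not the difficulty.

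**The case against.** The strongest objection is that d=0.6 and f=0.3 are one effect in two units: for two equal groups f = d/2. On that reading item 1 describes a group difference and says nothing about a mediator slope, so r=0.287 is the reviewer's choice. It also puts the true fall close to the cut-off, where a rule of this kind passes little more than half the time. This stands as a limit on the figures: 57% is conditional, not a value stated by the plan. It does not rescue the claim, because item 1 extends those sizes to every analysis and offers no others.

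A related objection concerns Hypothesis 4. The protocol describes cognitive control deficits as characteristic of schizophrenia, so a mediator difference larger than d=0.6 is plausible and the rule could then come near or above 80%. This also stands, and it is why the two hypotheses need separate figures.

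It can further be said that the slope is the real inferential test, and that the 25% rule only gauges degree. The slope test is indeed adequately powered at f=0.3. But a criterion labelled significant is a decision rule.

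Three stronger readings are tempting, and the documents support none of them:

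- **Comparing 39% with 80%.** A significant group difference, a significant slope and a fall above 25% occur together in 39% of trials. The plan claims no joint power and does not make Hypothesis 3 conditional on a significant Hypothesis 1 result. The two significance tests alone succeed together in only 63%.
- **Measurement error lowers the figures further.** The d and r used here are on the observed scale, so unreliability is already contained in them.
- **The study is too small.** For the Hypothesis 1 and 2 comparisons the sample size reproduces the stated power.

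**Conclusion.** The concern holds in a limited form. The 80% claim is correct for the Hypothesis 1 and 2 t-tests and, with f=0.3 taken as the slope effect, for the Hypothesis 3 and 4 slope tests. It is not correct for the 25% rule at the same sizes: about 57%, or 53% when a significant slope is also required.

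This rests on two-sided 0.05, d=0.6 on both CO and the mediator, and a within-group correlation of 0.287. The rule reaches about 80% if that correlation is near 0.40, or if the mediator differs by somewhere between d=0.8 and d=1.0. The plan states neither.

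Under the central assumptions a true mediator misses the threshold in about 43% of trials (1 − 0.57), so a miss carries little information. The plan does not say how a miss would be read. Misreading is a risk to guard against, not something the plan commits to.

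**What to change.** Reword item 1 of Sample Size and Data Analysis, along these lines:

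- With 45 completers per group, 80% power applies to the group comparisons under Hypotheses 1 and 2 at d=0.6 and, if f=0.3 is taken as the slope effect, to the slope tests under Hypotheses 3 and 4. State the alpha level and sidedness used.
- The >25% rule does not have 80% power at those sizes. Its probability of being met is about 57% (53% with a significant slope), assuming d=0.6 on outcome and mediator and a within-group correlation of 0.287.
- For Hypothesis 3, with d=0.6 on discrimination accuracy, give the range: 34% at a correlation of 0.20, 81% at 0.40, 93% at 0.50.
- For Hypothesis 4, give the range by size of the cognitive control difference at a correlation of 0.287: 57% at d=0.6, 76% at d=0.8, 87% at d=1.0. If the sponsor has grounds for particular values in either hypothesis, state them and the probability that follows.

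In item 2, add that a fall below the 25% threshold will be reported as inconclusive, not as evidence against mediation.

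This is a change of wording only. Enrolment, procedures and the analyses themselves stay as they are. The one cost is that a stated figure becomes less favourable.
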